NCT03756571

ANALYSIS PAN

Cerebral Palsy: Ankle Foot Orthoses - Footwear Combinations

August 7, 2018

Analysis Plan:

For both Specific Aims, our primary analysis will be an intent-to-treat analysis using outcomes collected during the parallel group RCT phase, (i.e., before TSAFO group crosses over to AFO-FC). This will be cross-sectional analysis based on linear regression models in which outcomes at primary endpoint of T1 (3-month) are the dependent variables, group indicator is the predictor of interest, with including baseline outcomes, and biomarkers of age, gender, gait pattern (equinus or crouch) and GMFCS. A secondary repeated measure analysis based on mixed effects models will also be conducted to examine the changes in outcomes across all 3 time points (T0, T1 and T2). In this analysis, group indicator will be entered as a time-varying predictor given the waitlist design (for AFO-FC group the indicators take values (0, 1, 1), whereas for TSAFO group the indicators take values (0, 0, 1)), time will be modelled as a discrete variable, and between group differences will be examined by group-by-time interactions and likelihood ratio test.

Study Design and Randomization.

A randomized waitlist trial [38] will be used to compare the AFO-FC to TSAFO (See Fig. 4). After enrollment, subjects are randomized to either wearing the AFO-FC (the intervention group) or TSAFO (waitlist group). There will be three main time points for assessment (T0, T1, T2) with the initial baseline assessment (T0) split over 2 visits. The first baseline visit includes consent, randomization, casting for orthoses (AFO-FC or TSAFO), and completion of parental report surveys (physical activity, function, satisfaction). For subjects in the intervention group, the second baseline visit includes attachment of accelerometer for 2 week assessment of community walking, fitting and tuning of new orthoses and shoes per AFO-FC algorithm, and gait analyses in barefoot and with AFO-FC. The intervention group return after two weeks of AFO-FC wear to check/adjust alignment using the VVGL, then wear the AFO-FC for three months before returning for their third assessment visit (T1). For subjects in the waitlist group, the second baseline visit includes fitting new TSAFO, attachment of accelerometer and gait analyses in barefoot and with TSAFO. They then wear

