Aim #1: Gait Deviation Index (GDI) and gait speed (Aim 1) will be assessed at the Orthocare Innovations 3DGA laboratory in Edmonds, WA. At the baseline second visit (T0), gait analyses will be conducted in random order at self-selected walking speed both barefoot and with either a TSAFO or the fit/tuned AFO-FC. Three months post fitting, final gait data is collected (T1) in random order at self-selected walking speed barefoot and with the AFO-FC for the intervention group or TSAFO for the waitlist group. During 3DGA, skin-mounted retro-reflective markers are placed on the child to collect the 3D joint/segment motions and forces using an 8-camera Vicon MX system with two integrated AMTI force platforms. Consistent with best practices in motion analysis that ensures consistency of motion data, markers will be attached by the same experienced lab personnel according to the Plug In Gait model and post-processing of all gait lab data carried out by one individual. Outcome data for each limb will be summarized by averaging all trials for each walking condition (barefoot and/or TSAFO and/or AFO-FC) during each study visit (minimum of 3 trials per condition). A single number, the GDI, is derived from the deviation of the subjects' data from a normal kinematic profile dataset of kinematic features including pelvic tilt/obliquity/rotation, hip flexion/extension and abduction/adduction, knee flexion/extension, ankle dorsiflexion/plantarflexion and foot progression [13].

In order to explore specific joint kinematic changes (Aim 1) with the AFO-FC versus TSAFO that contribute to the overall GDI, we will also calculate the Gait Profile Score (GPS) and Gait Variable Score (GVS) from the GDI. Similar to the GDI, the Gait Profile Score (GPS) represents the pattern of deviation as a single number and is derived from the same individual joint/limb gait kinematics as GDI. The GPS is calculated on all gait features via the root mean square difference between the subject's data and the average of the normative data set [13]. GVS, also a single number, can only be derived from the GPS and consists of nine joint/limb gait variables for each side of the body (i.e. sagittal knee flexion midstance with an overall score for the pelvis [52].

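### The SAP does not say which T0 gait condition is the baseline covariate for GDI and gait speed; if it is the braced one, it is post-treatment and shrinks the group difference

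*SAP*

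**What the plan says.** Order of events (SAP, Study Design and Randomization). Allocation comes first: "The first baseline visit includes consent, randomization, casting for orthoses (AFO-FC or TSAFO". Gait is recorded at the second baseline visit, when the assigned device is fitted. For the AFO-FC arm that visit covers "fitting and tuning of new orthoses and shoes per AFO-FC algorithm, and gait analyses in barefoot and with AFO-FC"; for the waitlist arm it covers "attachment of accelerometer and gait analyses in barefoot and with TSAFO".

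Gait conditions (SAP, Outcomes Measures, Aim #1). T0 gait is recorded "both barefoot and with either a TSAFO or the fit/tuned AFO-FC". The T1 conditions are again barefoot and the assigned device. The SAP lists no T0 gait trial in the child's previous orthosis.

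Primary model (SAP, Analysis Plan). The regression is set up so that "outcomes at primary endpoint of T1 (3-month) are the dependent variables, group indicator is the predictor of interest". It adjusts for the baseline value of the outcome and for four child characteristics: age, sex, type of gait pattern and GMFCS level. Neither the T1 condition used as outcome nor the T0 condition used as covariate is named.

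Secondary model (SAP, Analysis Plan). A mixed model uses a time-varying treatment indicator coded 0, 1, 1 for the AFO-FC arm and 0, 0, 1 for the TSAFO arm at T0, T1 and T2. Gait is not collected at T2.

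**The concern.** The SAP states that baseline and the 3-month visit use the same measures. The natural baseline partner of a braced T1 GDI is therefore the braced T0 GDI. That value is taken after randomisation, in the randomised device, so it is an early outcome and not a baseline. An orthosis acts mechanically once it is worn, so part of the difference between AFO-FC and TSAFO may already be present in it. Conditioning on it removes some of the contrast that the trial sets out to estimate.

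Both Aim 1 primary outcomes are exposed. A device that works at fitting and keeps its effect could look little better than TSAFO. Because the text leaves the choice open, two analysts could also estimate two different quantities from the same plan.

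**Working it through.** **1. The plan's own figure.** SAP, Power and Sample Size: 27 children give 80% power for a 5-point GDI difference between groups and 97% for 7 points. No SD, alpha or sidedness is stated. Assuming a two-sided 5% t-test with 14 versus 13 children, 80% at 5 points implies an SD of about 4.45, which predicts 97.5% at 7 points. The pair is consistent, and 27 / 0.9 = 30 reproduces the enrolment target. From here only the 5-point difference is used.

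**2. Formula.** Let D1 be the true group difference at T1, D0 the group difference already present in the covariate at T0, and b the within-arm slope of T1 on T0. The expected adjusted group coefficient is

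D1 − b × D0.

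Write D0 = f × D1, where f is the share of the effect present at fitting. The coefficient is then D1 × (1 − f × b).

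**3. Inputs.** D1 = 5 GDI points or 0.10 m/s, both from the SAP's power section. The values of b (0.5, 0.7, 0.8) and f (1, 0.5, 0) are assumptions.

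**4. Results.**

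| f | b | GDI coefficient | Speed coefficient (m/s) |
|---|---|---|---|
| 1 | 0.5 | 5 × (1 − 0.50) = 2.5 | 0.05 |
| 1 | 0.7 | 5 × (1 − 0.70) = 1.5 | 0.03 |
| 1 | 0.8 | 5 × (1 − 0.80) = 1.0 | 0.02 |
| 0.5 | 0.5 | 5 × (1 − 0.25) = 3.75 | 0.075 |
| 0.5 | 0.7 | 5 × (1 − 0.35) = 3.25 | 0.065 |
| 0.5 | 0.8 | 5 × (1 − 0.40) = 3.0 | 0.06 |
| 0 | any | 5.0 | 0.10 |

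Simulated regressions with 14 versus 13 children agree to within 0.05 of a GDI point. The f = 0 row is the case of a covariate that the device does not affect. It is the intended behaviour of barefoot T0.

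**5. Mixed model.** With no gait at T2, only T0 and T1 contribute. If braced T0 gait is entered, the AFO-FC arm is coded 0 at a visit where it was tested in the AFO-FC. A group-by-time contrast of change from T0 to T1 then estimates D1 − D0 = 5 × (1 − f): 0 points at f = 1 and 2.5 points at f = 0.5. The secondary analysis therefore cannot correct the primary one.

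**The case against.** *The SAP never selects braced T0.* This is right, and it sets the limit of the point. A reader might infer that the plan commits the analyst to a biased covariate. It does not: two T0 conditions are collected, the text says only "group indicator is the predictor of interest, with including baseline outcomes", and coding T0 as untreated fits the barefoot trial better. What stands is that the choice is open and that the like-for-like reading leads to the braced value.

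*Adjustment does not remove the whole immediate effect.* Correct. It removes slope times that effect, and all of it only at a slope of 1.

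*The effect may not be fully present at T0.* Also correct. The SAP schedules a re-evaluation two weeks after fitting, at which alignment may be adjusted, so f may be below 1. Direction also depends on persistence: if enough of the effect faded by T1, the coefficient could change sign and not merely shrink.

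*The target could be change over the wear period.* The SAP does speak of assessing the effect of wear. But the powered quantity is a between-group difference, and the primary model is described as cross-sectional at T1. This is a partial defence only.

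*Power.* A reader might infer a specific collapse in power. The documents do not support a figure, because they give no SD or alpha and the answer turns on what the back-solved 4.45 represents. With half the effect present, simulated power rises from about 62–64% to 74–76% between slopes 0.5 and 0.8 if 4.45 is the marginal SD. It falls from about 51–53% to 36–37% if 4.45 is the residual SD. No power loss is therefore claimed.

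*The Protocol has a baseline gait trial in the current orthosis.* It does, under Gait Analyses, but for a single-group pre/post study of 10 children. The SAP defines its own T0 conditions and includes no such trial.

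**Conclusion.** The concern holds in conditional form. The SAP leaves the T0 gait condition unspecified, and one of the two available conditions is a post-treatment measurement. If braced T0 is used, a 5-point GDI difference is estimated as 1.0 to 2.5 points when fully present at fitting, or 3.0 to 3.75 points when half present, for slopes of 0.8 down to 0.5. If barefoot T0 is used, this bias does not arise.

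The size rests on assumed slopes and immediate shares and on an effect of equal or greater size at T1. The formula itself needs only that D0 and b are not zero. Coding the AFO-FC arm as 0 at T0 is wrong for braced T0 gait whatever the size of the effect. The point covers GDI and gait speed only. It is not extended to the surveys, which are completed at the first baseline visit before fitting, or to StepWatch.

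**What to change.** In the Analysis Plan:

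- State that the Aim 1 dependent variables are braced GDI and braced gait speed at T1.
- Name barefoot GDI and barefoot gait speed at T0 as their baseline covariates, and state that braced T0 gait is not used as a covariate.
- Report braced T0 gait as a separate outcome, the immediate effect at fitting, adjusted for barefoot T0.
- Do not enter braced T0 gait in the mixed model with the AFO-FC indicator at 0.

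The cost is SAP wording only, since barefoot gait is already recorded at T0. There is one statistical downside: barefoot T0 may correlate less with braced T1 than braced T0 does, so less residual variance may be removed. The documents do not allow that loss to be quantified. The fix also assumes that the barefoot T0 trial, which takes place at the fitting visit in random order with the braced one, is not itself altered by brief wear of the device.

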the new TSAFO for three months before returning for their third assessment visit (T1) after which they cross-over to the intervention group and undergo the same protocol as the original intervention group. The same outcome measures are administered at baseline and 3 months post fitting (T1) to assess effect of AFO-FC or TSAFO wear. At 6 months post fitting (T2), all outcomes except gait analyses are collected again to assess retention (T2).

To ensure internal validity of treatments and address reported parental concerns (See C.3. Aim #1), all orthoses will be cast, fit and tuned by a single study orthotist and PI. Cascade Orthotics, Bellingham, WA, USA, will fabricate all orthoses. Standardized shoes will be provided to minimize challenge of finding shoes for both TSAFO and AFO-FC. The PI and study orthotist will meet weekly to review quality of devices, fitting and tuning of all orthoses/shoes. A single orthotist will make all the orthoses, which will keep fabrication, (i.e. material thickness, trim lines), consistent. Consistency of AFO-FC prescription will be further facilitated by use of a published decision tree [8, 37] that the PI has experience (6 years) implementing within clinical practice at Seattle Children's Hospital. The local study team will meet monthly to review enrollment data, data collection logistics, and data quality (survey/gait lab/StepWatch). This information will then inform any adjustment to the protocol needed to troubleshoot challenges and ensure valid data collection and study completion. Per the decision tree and confirm internal validity of the AFO-FC intervention, a single video vector gait lab (VVGL) re-evaluation will occur 2 weeks post initial fitting to adjust and confirm that a "clinically optimal AFO-FC" was obtained. Optimal AFO-FC is defined as when thigh alignment in static standing is as close to vertical as active and passive hip and knee range of motion allow, the child can attain and maintain this posture spontaneously, and approximation of this alignment is observed during midstance of gait [39, 40] (Fig. 3).

Participant Characteristics.

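### The secondary mixed model gives waitlist children at T2 the same treatment code as AFO-FC children with three or six months of wear, although on the stated schedule they have three months at most

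*SAP*

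**What the plan says.** All of this is in the SAP. The Protocol describes a pre/post study of 10 children with one follow-up visit and no crossover, so it does not settle the timing.

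- **T1** (Study Design and Randomization): "The same outcome measures are administered at baseline and 3 months post fitting (T1) to assess effect of AFO-FC or TSAFO wear". Fitting here means the first study device in either arm.
- **T2** (same section): "At 6 months post fitting (T2), all outcomes except gait analyses are collected again to assess retention (T2".
- **Waitlist arm** (same section): these children wear "the new TSAFO for three months before returning for their third assessment visit (T1) after which they cross-over to the intervention group". They then "cross-over to the intervention group and undergo the same protocol as the original intervention group".
- **The protocol they join** (same section): "The first baseline visit includes consent, randomization, casting for orthoses (AFO-FC or TSAFO"), with fitting at a second visit. After that, "The intervention group return after two weeks of AFO-FC wear to check/adjust alignment using the VVGL, then wear the AFO-FC for three months".
- **Secondary model** (Analysis Plan): the time-varying indicator is (0, 1, 1) for the AFO-FC arm, "whereas for TSAFO group the indicators take values (0, 0, 1"). Time is discrete, and there is no term for duration of wear. The same paragraph says that between-group differences will be examined by group-by-time interactions and a likelihood ratio test.

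**The concern.** At T2 the two arms differ in AFO-FC exposure by about three months or more, yet the indicator gives them the same value. It also equates both with the intervention arm at T1. If the effect of the AFO-FC changes with wear, the coefficient is not the effect at any defined duration.

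T2 is also described as measuring retention. That fits the intervention arm, which continues in a device worn since T0. For the waitlist arm T2 follows a first exposure, so pooling the arms mixes two questions.

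At stake is the secondary repeated-measures analysis of outcomes collected at T2: StepWatch walking activity, the Pediatric Balance Scale and the parent reports.

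**Working it through.** **1. Schedule.** Take 3 months as 13 weeks and 6 months as 26 weeks, counted from the first fitting. Let L be the weeks from T1 to the waitlist child's AFO-FC fitting. The SAP does not give L, so the values below are assumptions.

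Waitlist AFO-FC wear at T2 = 26 − 13 − L = 13 − L weeks. Three months of wear needs T2 at 13 + L + 13 = 26 + L weeks.

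| L (weeks, assumed) | Waitlist wear at T2 | Intervention wear at T2 | T2 needed for 13 weeks of waitlist wear |
|---|---|---|---|
| 0 | 13 | 26 | week 26 |
| 2 | 11 | 26 | week 28 |
| 4 | 9 | 26 | week 30 |
| 6 | 7 | 26 | week 32 |

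The stated T2 gives waitlist children three months of wear only if L = 0. If the two-week check comes before the three months, instead of falling inside them, each required T2 is two weeks later.

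**2. What the indicator assumes.** Its values equal (group × T1) + T2:

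- AFO-FC arm: (0,1,0) + (0,0,1) = (0,1,1).
- TSAFO arm: (0,0,0) + (0,0,1) = (0,0,1).

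With discrete time in the model, the T2 part is absorbed by the time effect and only group × T1 remains. The model therefore allows a treatment difference at T1 and none at T2, beyond any baseline difference that a group main effect would carry.

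**3. Adding the group-by-time terms.** An intercept, two time terms, group, two group-by-time terms and the indicator make 7 columns of rank 6. The indicator is then redundant. The paragraph thus describes two different models: one imposes equality at T2, and the other does not need the indicator.

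**4. Effect on the coefficient.** Let d0, d1 and d2 be the true between-group differences at T0, T1 and T2, and let rho be the within-child correlation. With a random intercept, shared time effects, the indicator and no group main effect, generalised least squares gives

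estimate = d1 − [rho/(1 + rho)] × (d0 + d2).

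Set d0 = 0, d1 = 1 (the 13-week effect) and rho = 0.5, so the multiplier is 0.5/1.5 = 1/3.

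*Benefit linear to 13 weeks, then flat.* d2 = 1 − (13 − L)/13 = L/13.

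- L = 2: 1 − (1/3)(2/13) = 0.95
- L = 4: 1 − (1/3)(4/13) = 0.90
- L = 6: 1 − (1/3)(6/13) = 0.85

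*Benefit linear to 26 weeks.* d2 = 2 − (13 − L)/13 = 1 + L/13.

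- L = 0: 1 − (1/3)(1) = 0.67
- L = 2: 1 − (1/3)(15/13) = 0.62
- L = 4: 1 − (1/3)(17/13) = 0.56
- L = 6: 1 − (1/3)(19/13) = 0.51

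In this second case most of the loss comes from giving three and six months one code, since it is already a third at zero lag.

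*Sensitivity to rho.* If the T2 difference is 25% of the T1 effect, the coefficient is 94%, 92% or 90% of that effect at rho 0.3, 0.5 or 0.7. If it is 50%, the figures are 88%, 83% and 79%.

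**The case against.** **Which fitting starts the clock.** The SAP never says which fitting anchors T2 for a child fitted twice, and the design figure it cites (Fig. 4) is not in the text available for review. A reader might infer that the schedule is impossible or flatly contradictory. The documents do not go that far: with L = 0 and the check inside the three months, it works. But restarting the clock at the AFO-FC fitting would put waitlist T2 at nine months or more after the first fitting, which does not match a shared discrete T2. Either reading needs a clarification.

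**The two-week check.** It might be counted as extra time. The SAP elsewhere places the check two weeks after initial fitting and T1 three months after fitting, so it can fall inside the three months. The shortfall below three months then rests on L alone. The SAP also does not say in terms that AFO-FC casting of waitlist children waits until after T1; it describes baseline casting for one device or the other. This stands.

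**The size.** Under linear accrual, waitlist children would have 11/13, 9/13 or 7/13 (85%, 69% or 54%) of the 13-week effect at T2 for lags of 2, 4 or 6 weeks. A reader might take these as the bias. They are an assumed effect in one arm at one visit. With a plateau at 13 weeks and rho 0.5, the coefficient loses about a third as much.

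**The interactions.** If the analysis relies on group-by-time terms, equality at T2 is not imposed and the coefficient bias does not arise. That is correct, but the indicator then does nothing, and the SAP specifies both.

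**Moving the waitlist visit.** Matching waitlist T2 to three months of wear would leave three months coded the same as six, and would place T2 at different elapsed times in the two arms.

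**Conclusion.** The point holds for the secondary mixed model and for the retention reading of T2. On the plain one-clock reading, intervention children have about 26 weeks of AFO-FC wear at T2 and waitlist children 13 weeks at most, and the indicator treats them as equal. This mismatch exists even at zero lag; any lag widens it.

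The bias cannot be fixed from the documents, because neither the lag, nor the correlation, nor the course of benefit with wear is given. As an illustration, the coefficient is 95% to 85% of the T1 effect for lags of 2 to 6 weeks with a plateau at 13 weeks, and 62% to 51% if benefit grows linearly to 26 weeks, both at rho 0.5. If benefit is complete within the waitlist arm's shorter wear and is then held, there is no bias.

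A reader might infer that the trial's main result is compromised. It is not. The primary analysis for both aims is the T1 comparison before crossover. Gait analyses are not repeated at T2, so GDI and laboratory gait speed are untouched, as is the stated power. The matter should be settled before the secondary analysis is run.

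**What to change.** 1. **Reconcile the schedule.** State which fitting anchors T2 for waitlist children, and give a visit window.
2. **Record the date of each child's AFO-FC fitting**, so that wear at every assessment is known.
3. **Change the secondary model.** Either replace the 0/1 indicator with duration of AFO-FC wear, or use group-by-time terms without the indicator so that the T2 contrast is free. The second assumes less, because a linear wear term would itself be wrong if benefit levels off. In that model the T1 contrast compares devices, and the T2 contrast compares longer with shorter AFO-FC exposure.
4. **Report retention (T1 to T2) from the original AFO-FC arm only**, and report waitlist T2 as first exposure, with the observed weeks of wear.

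The cost is SAP wording, one recorded date per child and slightly less precision from the freer model. The retention estimate would rest on about half the sample (about 15 of the 30 enrolled if allocation is equal, before attrition). It would be a within-arm change without a concurrent control, and should be described as such.

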AIM #2: The primary outcome of community walking activity will be captured with the ankle worn StepWatch (SW) accelerometer with balance quantified using the Pediatric Balance Scale. Parental report will capture physical activity with the Activity Scale for Kids – Performance version (ASKp), activity, fatigue and pain with selected items from the Patient-Reported Outcomes Measurement

Information System (PROMIS) and satisfaction with devices via the Orthotic and Prosthetic Users' Survey (OPUS). StepWatch (SW) – A pager sized accelerometer worn on the ankle, the SW, has one of the highest levels of accuracy for detecting steps across walking speeds from among commercially available monitors. SW daily stride levels for typical children and a large cohort with CP have been documented.

Power and Sample Size:

We will power this exploratory study based on our case series data (n=4, Fig. 5), published MCID for the Aim #1 primary outcomes of GDI and gait speed and published data for walking activity in CP [1, 45, 50]. A total sample size of 27 would allow 80% power to detect a 5 point GDI difference between groups with 97% power for a 7 point difference (MCID = 4.3 to 5.0) [45, 49] between TSAFO and AFO-FC. This sample size will have 83% power to detect a 0.10 m/sec difference in gait speed between groups with 95% power for a 0.15 difference (MCID=0.10 m/sec [50]) between conditions. A sample size of 27 has >99% power to detect a 2,000 strides/day treatment condition difference per StepWatch. This is based on the PI's cross-sectional StepWatch strides/day data from 134 youth with CP (GMFCS level II, n=84; level III, n=50; ages 2-14 years) with a mean difference between GMFCS levels of 1,630 strides (SD=2100) [1]. Therefore, we will enroll 30 participants to account for 10% attrition.

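### The two gait-speed power figures for n=27 (83% at 0.10 m/s, 95% at 0.15 m/s) cannot both be right on one basis, and the text does not show which is wrong

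*SAP*

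**What the plan says.** The SAP's Power and Sample Size section bases its figures on several sources. It opens "We will power this exploratory study based on our case series data (n=4, Fig. 5", and goes on to cite "published MCID for the Aim #1 primary outcomes of GDI and gait speed" and published walking-activity data.

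For GDI it says: "A total sample size of 27 would allow 80% power to detect a 5 point GDI difference between groups", and gives 97% for 7 points. For gait speed the next sentence refers to the same sample size and claims "83% power to detect a 0.10 m/sec difference in gait speed between groups with 95% power for a 0.15 difference". Its second part runs on in full as "95% power for a 0.15 difference (MCID=0.10 m/sec [50]) between conditions". The first gait-speed difference is therefore labelled as between groups and the second as between conditions.

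The readable text gives no gait-speed SD, and no alpha, sidedness or test for the power calculation. Fig. 5, which is not shown, may hold an SD. The Protocol does not help: its Sample Size section describes a pre/post study of 10 children with no power calculation.

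**The concern.** Power at two differences is tied together once the sample size, SD, alpha and test are fixed. Raising the difference by half, from 0.10 to 0.15 m/s, raises the standardised effect by half. Starting from 83%, that should take power close to 100%. A rise of only 12 points, to 95%, is too small.

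A reader will use this sentence to judge whether the trial can detect the MCID for gait speed. If the 83% is sound, only the 0.15 m/s entry is off and power at the MCID is adequate. If the 95% at 0.15 m/s is sound, power at the MCID is below 80%.

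**Working it through.** **Inputs from the SAP (Power and Sample Size).** n = 27 in total; gait speed 83% at 0.10 m/s and 95% at 0.15 m/s; GDI 80% at 5 points and 97% at 7 points.

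**Assumptions.** Two-sided alpha 5% (range 1% to 20% below); a 13/14 split; one fixed SD and one test for both entries. The printed powers cannot be reproduced from their inputs because no SD is given. What can be tested is whether each pair agrees with itself, since the SD and n then cancel.

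**Formula (normal approximation).** Power = Φ(δ/SE − z_α), so δ/SE = z_α + z_power. Here z_0.975 = 1.960, z_0.80 = 0.842, z_0.83 = 0.954 and z_0.95 = 1.645.

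**Control: the GDI pair.**
- 80% at 5 points: δ/SE = 1.960 + 0.842 = 2.802.
- At 7 points: 2.802 × 7/5 = 3.922; power = Φ(3.922 − 1.960) = Φ(1.962) = 97.5%. The SAP states 97%, so this pair is coherent.

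**Gait speed, starting from 83% at 0.10 m/s.**
- δ/SE = 1.960 + 0.954 = 2.914.
- At 0.15: 2.914 × 1.5 = 4.371; power = Φ(2.411) = 99.2%. The SAP states 95%.

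**Gait speed, starting from 95% at 0.15 m/s.**
- δ/SE = 1.960 + 1.645 = 3.605.
- At 0.10: 3.605 / 1.5 = 2.403; power = Φ(0.443) = 67.1%. The SAP states 83%.

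**Keeping both powers and the 0.10.** The second difference is 0.10 × 3.605/2.914 = 0.124 m/s. The SAP states 0.15.

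**Noncentral t (25 df), by alpha:**

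| Two-sided alpha | Power at 0.15, given 83% at 0.10 | Power at 0.10, given 95% at 0.15 | Difference giving 95% (m/s) | SE ratio needed if contrasts differ |
|---|---|---|---|---|
| 1% | 99.7% | 59.6% | 0.120 | 1.25 |
| 5% | 99.2% | 67.2% | 0.124 | 1.21 |
| 10% (one-sided 5%) | 98.8% | 70.9% | 0.127 | 1.18 |
| 20% | 98.1% | 74.9% | 0.131 | 1.15 |

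The last column is 1.5 × (δ/SE for 83%) / (δ/SE for 95%); the normal version at 5% is 1.5 × 2.914/3.605 = 1.21. Using 20 or 26 df leaves the 5% row at 99.2% and 67.2%.

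**Rounding.** At 5%, 82.5% to 83.5% at 0.10 gives 99.1% to 99.3% at 0.15; 94.5% to 95.5% at 0.15 gives 66.0% to 68.4% at 0.10.

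**Alpha that would reconcile them.** Setting 1.5(z_α + 0.954) = z_α + 1.645 gives z_α = 2(1.645 − 1.431) ≈ 0.43, a one-sided alpha of about 0.33. Nobody would plan on that.

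**Implied SDs (t, 13/14 split, two-sided 5%).** 0.086 m/s from the first entry and 0.104 m/s from the second. No single SD serves both.

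**The case against.** **Two contrasts.** The shift from groups to conditions may mean that the second power belongs to another comparison. The SAP's Outcomes Measures section does use condition more broadly, in "averaging all trials for each walking condition (barefoot and/or TSAFO and/or AFO-FC) during each study visit". This cannot be excluded, so the finding stays conditional. The text gives it little support, however. The GDI sentence also changes its label, ending on TSAFO versus AFO-FC, and its pair is coherent. A second contrast would need a standard error about 1.21 times the first, and a within-child comparison would not normally supply that. With equal SDs, pairing all 27 children gives a ratio of 0.71 at zero correlation and 0.50 at correlation 0.5. Pairing only 13 at zero correlation gives 1.02. If conditions simply means TSAFO versus AFO-FC, it is the group contrast again and the inconsistency stands.

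**Uncertain SD.** Averaging power over the uncertainty in an SD from four children would flatten the curve. Under a normal approximation, 83% at 0.10 leads to about 94% at 0.15 with 3 df and 96% with 6 df, either side of the printed 95%. No such method is described, and it would put GDI power at 7 points at about 91% to 93%, against 97% stated. It is unlikely, but it does limit the claim to a fixed SD.

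**Unseen text.** Fig. 5, or a part of the source document not included here, may give the SD, alpha and test. That is a fair caution about calling those items missing. It does not rescue the pair, since no single fixed SD makes both entries true at a conventional alpha.

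**Weight.** The study is called exploratory, the GDI figures support n=27 on their own, and on one reading the only error understates power at 0.15 m/s. All of this stands, and it limits the consequence to the gait-speed statement.

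**Conclusion.** The concern holds, conditional on one fixed SD, one test and one conventional alpha for both entries, which is what tying them to a single sample size implies. At an assumed two-sided 5%, one of three printed figures is then wrong: the 95% (about 99% implied), the 83% (about 67% implied), or the 0.15 m/s (about 0.124 implied). Otherwise, two contrasts were reported as one. Neither the allocation nor a paired or parallel test changes this, provided both entries share it. The documents do not favour any one explanation, so power at the 0.10 m/s MCID is unresolved and not shown to be inadequate. The case for n=27 from GDI is untouched.

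**What to change.** In the SAP's Power and Sample Size section, state for both gait-speed entries the SD and its source (pointing to Fig. 5 if it is there), the alpha, the sidedness, the test, and whether the contrast is between groups or between conditions. Recompute both powers on that single basis, confirm that 0.15 m/s is the intended second difference, and replace the printed pair. If power at 0.10 m/s comes out below 80%, say so. If two contrasts were intended, describe each with its own SD and test.

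Suggested wording: *Assuming a gait-speed SD of [x] m/s ([source]), n=27 and [one/two]-sided alpha [y], a [test] of the [between-group/between-condition] difference has [p1]% power for 0.10 m/s and [p2]% for [0.15] m/s.*

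The cost is one recalculation and one rewritten sentence, with no change to enrolment, endpoints or analysis. The only downside is that the stated power at the MCID may turn out less favourable.
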